and replication, a former cornerstone of the scientific method, has now been largely superseded by single large multinational studies. This lack of replication[18] as well as concerns of possible interactions between studies drug intervention and different healthcare systems can result in residual uncertainties even following “positive” results from large, single, comparative RCT evaluations[11, 12]. Conventional RCTs also have important limitations including inclusion/exclusion intricacies with recruitment difficulties, complexities in implementation, incomplete follow-up (especially for side effects) and high cost[17]. These limitations often reduce the feasibility of performing RCTs in everyday practice with a consequence that many routine practices are never fully evaluated or confirmed. While non-experimental methodologies can provide information in a more cost-efficient manner, the associated uncertainties, often principally but by no means limited to confounding by indication bias, is such that the gold standard design for drug assessment remains randomization. The “trick” to increasing RCTs is to employ both novel RCT designs and analytical elements to address these barriers and make trials more clinically and economically feasible.

As individual randomization may be difficult in situations where there are many clinicians involved in patient care and when rapid access to care is a priority, we have elected to use the novel pragmatic RCT cluster randomization (CR) design. This design resolves these issues and enhances practicality, efficacy, and bias reduction. A variation of the parallel group CR design is the cluster randomized crossover (CRXO) design which will control any temporal trends which might occur, for example with the rapidly evolving PCI technology. We are therefore proposing a CRXO design whereby a single center will perform 6-10 cluster periods each of 2 months duration during which all patients will receive one of the two allotted treatments regimes.

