The CRXO design will simplify trial conduct, enhance overall recruitment, and generalizability while maintaining study integrity. The merits of the CRXO design have been increasingly appreciated with recent publications in several high impact journals[19, 20]. RCTs with individual randomization is logistically difficult in situations where there are many acute caregivers and where patients may be recruited in a 24X7 emergency environment as with ACS. CR, by simplifying the mechanics of randomization, avoids these problems as well as the potential bias of cross contamination while maintaining the integrity of randomization. Given that the division of cardiology (Chief of Cardiology support letter in the Appendix) has agreed that equipoise exists regarding these competing interventions, all patients who are candidates for DAPT will be eligible for the study. Also CRXO importantly portends that individual informed consent for an ACS trial can be obtained in a less urgent setting, permitting more detailed information sharing and a more thorough and meaningful researcher / patient dialogue to occur.

A CR trial usually requires a larger sample size to achieve the same power as a standard RCT due to possible correlated measures with the clusters, measured by the intraclass correlation coefficient (ICC). In our trial, the marked increased recruitment possibilities will more than compensate for this minimally decreased power. The CRXO design increases efficiency over standard CR studies. and importantly controls for any secular trends in concomitant therapies. CR trials do have diminishing returns in power and precision as cluster size increases but this may be mitigated by increasing the number of clusters as with a CRXO design[21]. The CRXO design can achieve up to 50% better power than the standard CR design[22]. Analyses must also account for the clustering to avoid the bias of overly precise estimates of the treatment effect.

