will also be consented to consult their electronic health records at 1 and 3 years post randomization. The ability to measure long term outcomes at 3 years, via electronic databases, is another distinctive aspect of the study and will offer a unique opportunity to assess the long term consequences of different DAPT strategies following an ACS. While the main objective of this project is the evaluation of clinical effectiveness and safety outcomes, the expertise of the team will permit future ancillary investigations into quality of life and economic sub-studies. The project will also provide unique training and research opportunities for graduate students.

Sample size calculations

As there is some similarity between individuals within the same cluster, both within the same time period and across different time periods, CR trials require an increased sample size compared to a standard individual parallel group RCT. This loss of efficiency is more than offset by a more comprehensive patient recruitment. In addition to effect size and variation, CRXO sample size calculation depends upon the number of clusters, the size of the clusters, the number of time periods, and the similarity between individuals (both within and between clusters) as measured by the ICC. Assuming the event rates recorded in PLATO (12% vs. 10%), type 1 and type 2 errors of 5% and 20% respectively, power calculations for a standard individual randomized trial approach would suggest the need for 1,500 patients in each arm. For a CR trial, calculations using R (library(CRTsize) suggests that we need 6 clusters of 400 patients for each arm (total 4800, larger sample size due to ICC). However CRXO design has been shown to increase the statistical efficiency over the standard CR design[22]. The Figure below shows that 5 clusters for each arm (total sample size 4000) will provide greater than 80% power[21], suggesting that our 18-month recruitment period will be sufficient. Given our current annual angiogram / PCI volume and with the expected additional 10% of potential recruited ACS patients coming from the hospital CCU without an angiogram, we should have the capacity to meet our power calculations within an 18 month recruitment period based on the excellent (>90%) recruitment rates observed in other pragmatic comparative effectiveness trials[36].

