In addition to a standalone analysis, our main Bayesian analysis will incorporate the 1800 PLATO NA patients as our prior distribution, essentially providing a > 50% safety margin for our sample size calculations (see next section).

Statistical analysis

[figure not shown]
The trial data will be analyzed following the intention to treat principal. Clustered data require appropriate advanced statistical techniques that accounts for the likeness of cluster members, otherwise analysis can lead to overly precise estimates and potentially incorrect inferences about the effectiveness of the intervention.

Appropriate analysis will involve generalized estimating equations and hierarchical models. Bayesian analyses will be performed using JAGS [37] version 3.4.0 and R [38]. All Markov Chain Monte Carlo simulations will be run on two chains with 10 000 iterations discarding the first 1000. Convergence will be monitored using CODA [39] and checked by observing the traces of posterior samples, and by inspecting the Gelman-Rubin R statistic [40] and the Raftery-Louis diagnostics.[41]

Our primary analysis will involve a Bayesian approach that synthesizes all the pertinent evidence concerning these DAPT regimes by incorporating our prior information (PLATO data) with the likelihood of the current data. The advantages of this approach include a mathematically rigorous and exact combination of the totality of the data allowing direct probability statements about the relative strengths of the two regimes (statements that are desired by clinicians and decision-makers but which are technically impossible with the usual frequentist (p value) approach). The strength of this approach is displayed graphically and is described more fully in the next section. We will also perform a “standalone” Bayesian analysis by using a non-informative prior so that results driven uniquely by the data from this proposal may be appreciated.

Anticipated results and conclusions

Concretely the question remains which PLATO data shall we use for the prior data, the whole dataset or that limited to the NA subgroup. Our Bayesian approach will examine the robustness of the data by considering both! First, consider in the Figure (top) what might be called the “enthusiastic” prior which uses all the data and shows the overall benefit with ticagrelor.

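### GEE in its usual form is too precise for 6 to 10 cluster periods: a nominal 5% test rejects a true null about 12-13% of the time with 9-10 periods and about 18% with 6

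*Protocol*

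**What the plan says.** - **Design (Protocol, Methods):** "a single center will perform 6-10 cluster periods each of 2 months duration", each period allotted to one of the two regimens.
- **Size (Sample size calculations, Study timeline):** the power statement uses 5 clusters per arm and 4,000 patients, which is 400 per period. Recruitment is projected at 18 to 20 months, which is 18/2 = 9 to 20/2 = 10 two-month periods.
- **Aim (Methods):** "Analyses must also account for the clustering to avoid the bias of overly precise estimates of the treatment effect". The Statistical analysis section repeats the warning.
- **Method (Statistical analysis):** "Appropriate analysis will involve generalized estimating equations and hierarchical models". No unit of clustering, variance estimator or reference distribution is named for the GEE, and its role is not defined. The primary analysis is Bayesian with a PLATO prior, with a standalone Bayesian analysis under a non-informative prior.
- **Error rates (Sample size calculations):** "type 1 and type 2 errors of 5% and 20% respectively".

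**The concern.** With one hospital, the hospital cannot be the GEE cluster: a single cluster gives no usable sandwich variance. The cluster period is the only workable unit, so the data contain 6 to 10 independent units however many patients are enrolled.

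The usual GEE test is justified by a large number of clusters. With 3 to 5 per arm it fails in two ways. The sandwich variance is too small on average, and the normal critical value ignores the few degrees of freedom behind that variance. Both make the analysis look more precise than it is, which is the fault the protocol sets out to avoid. At stake is the false-positive rate of any GEE-based test and the coverage of any GEE-based interval.

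**Working it through.** **Inputs.** From the protocol: 6 to 10 periods in one centre; 400 patients per period (4,000/10); type 1 error 5%; event rates 12% and 10%, so a common rate near 11% under the null. Assumed: a two-sided test (sidedness is not stated); an even split of periods (5/4 with 9); the period as cluster; independent periods; an ICC of 0 to 0.05, because the protocol names the ICC but gives no value.

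**The plan's own figure.** The plan gives no rejection rate for GEE. The benchmark is its nominal 5%. The 1,500 per arm for an individually randomised trial does not enter this check. It does not reproduce either (12% vs 10% at 80% power needs about 3,841 per arm, two-sided), but that is a separate matter.

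**Step 1: bias of the variance.** With k equal periods per arm, the treatment effect is a difference of two means of k period-level values. The uncorrected sandwich divides each arm's sum of squares by k instead of k-1, so its expectation is (k-1)/k of the true variance: 4/5 with 10 periods, 2/3 with 6.

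**Step 2: rejection rate.** The correctly scaled statistic follows t with 2k-2 df, and the GEE z statistic is that value times sqrt(k/(k-1)). So

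P(reject) = P(|t(2k-2)| > 1.96 × sqrt((k-1)/k)).

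| Periods | Threshold on t | df | Rejection rate |
|---|---|---|---|
| 6 (3/3) | 1.600 | 4 | 18.5% |
| 8 (4/4) | 1.697 | 6 | 14.1% |
| 9 (5/4) | by simulation | – | 13.0% |
| 10 (5/5) | 1.753 | 8 | 11.8% |

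**Step 3: check on binary data.** Beta-binomial simulation of logistic GEE (200,000 replicates per scenario, 400 per period, ICC 0 to 0.05) gave 11.8-13.0% with 10 periods and 18.5-19.8% with 6. The mean standard error was 0.83-0.86 of the true SD with 10 periods and 0.72-0.77 with 6. Fitting GEE directly with standard software (1,000 data sets each, exchangeable correlation, default robust errors, ICC 0.01) gave 11.4% and 19.5%.

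**Step 4: what restores 5%.**

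| Method | 10 periods | 6 periods |
|---|---|---|
| Uncorrected sandwich, z | 11.8% | 18.5% |
| Unbiased variance, z | 8.6% | 12.2% |
| Uncorrected sandwich, t | 7.3% | 8.6% |
| Kauermann-Carroll type, t on K-2 df (simulated) | 5.0-5.7% | 5.0-5.3% |
| Mancl-DeRouen, t on K-2 df (simulated) | 3.3-3.8% | 2.7-2.8% |

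K is the total number of periods. Either correction alone is not enough.

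**Step 5: price in interval width.** Valid width relative to the usual GEE width is sqrt(k/(k-1)) × t(0.975, 2k-2)/1.96:

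- 10 periods: sqrt(5/4) × 2.306/1.96 = 1.32
- 6 periods: sqrt(3/2) × 2.776/1.96 = 1.73

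**The case against.** **The protocol does not say the GEE will be uncorrected.** This is the strongest point on the other side. Small-sample variance and degrees of freedom are often left to a SAP, and none is shown. GEE with a correction and a t reference would satisfy the quoted sentence. This stands to the extent that a reader may not infer a commitment to an uncorrected test. What remains is that the protocol offers GEE as adequate for a design it fixes at 3 to 5 units per arm, in a section that goes down to the number of chains and the burn-in. In its ordinary form the method defeats the stated purpose.

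**The primary analysis is Bayesian.** This stands. A reader might infer that the posterior intervals are too narrow as well, but the documents do not support that. The non-informative prior in the protocol is the alternative to the PLATO prior; nothing says it is the prior on the between-period variance. In simulations of a period-level hierarchical model (400 per period, 11% event rate, flat prior on the effect, assumed ICC 0 to 0.01), a uniform(0, 5) prior on the between-period SD made the 95% interval exclude a true null in at most about 2% of trials with 6 periods and 4-5% with 10. That is conservative. A tight half-normal prior (scale 0.2) gave about 10-11% and 8% at ICC 0.01. The direction depends on a prior the protocol does not state.

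**The 18% is the edge case.** This is fair. The power statement and the timeline point to 9 or 10 periods, so 12-13% is the relevant figure; 18% applies only at the low end of the stated range.

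**Six periods can still be tested validly.** This also stands. A reader might infer that 6 periods allow no convincing test, because a two-sided randomisation test on a 3/3 split cannot go below 2/C(6,3) = 2/20 = 0.10. That floor belongs to that test alone. A period-level t-test on 4 df holds 5% and has no such floor.

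**Conclusion.** The point holds for GEE-based tests and intervals. With the cluster period as the unit, an uncorrected sandwich variance and a z reference, the true two-sided error rate is about 12-13% with 9-10 periods and about 18% with 6, against a nominal 5%. The result hardly changes over ICC 0 to 0.05, so the missing ICC value does not weaken it. It rests on independent periods of equal size, split as evenly as possible.

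It does not show that a correction is absent from an unseen SAP, that the primary Bayesian posterior is too narrow, or that the 6-period option has to be removed. For the hierarchical model the supported statement is narrower: 6 to 10 periods inform the between-period SD weakly, so its prior can matter to the result. The plan should be changed, but the primary analysis is not overturned.

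**What to change.** 1. State that the cluster period is the unit of clustering.
2. For any frequentist analysis, specify one of two methods: period-level summaries with a t reference on periods minus 2 df (fewer if time terms are fitted), or GEE with both a small-sample variance correction and a t reference. A Kauermann-Carroll type correction held the level closely here; Mancl-DeRouen was somewhat conservative.
3. For the hierarchical model, state the prior on the between-period SD and report the result over a stated range of priors, from diffuse to tight. A single tight prior can itself make the interval too narrow.

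**Cost.** Only the analysis wording changes; design and data collection do not. The price in precision is real: valid intervals are about 1.3 times as wide as the usual GEE intervals with 10 periods and 1.7 times with 6. That should be acknowledged when the precision of a GEE result is discussed.

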However, the FDA by approving the drug ultimately did not share that view. Unfortunately, the FDA did not provide any qualitative logic or guidance on how they integrated these apparently disparate results and arrived at their regulatory decision. The conventional statistical model used in the PLATO analysis subsumes that every patient, regardless of differences in recruitment characteristics or ancillary treatment strategies received in the different regions, is completely identical in their response to the studied intervention. It seems highly unlikely that patients from the 43 PLATO enrolling countries are truly identical in their drug response given recruitment, genetic and background treatment variations. For example, while not reported in the original NEJM article[9], the FDA review shows a statistically significant negative interaction between ticagrelor and early PCI (HR 1.32, 95% CI 1.02 - 1.73). In other words, patients undergoing early PCI has worse outcomes when randomized to ticagrelor. As early PCI is the norm in NA patients, this raises the distinct possibility that the overall superiority results with ticagrelor in PLATO study may not be applicable to NA patients. While this or any other subgroup analysis does not prove that interactions between the interventions and the health care system exist, it does support the notion that such potential interactions merit at least serious reflection and thoughtful consideration. The question then becomes how to weight the relative strengths of a consolidated single analysis of all the data (an underparameterized model) with a separate analysis that considers each group to be completely independent (an overparameterized model)?

A method to sort out this conundrum is hierarchical analysis. This method by considering the subgroups not to be identical but rather exchangeable avoids being restricted to the extreme interpretability positions of considering all regions to be identical or totally distinct. Hierarchical analysis defaults to the identity model when there is no between group variability. As the between group variability increases so does the weight given to each separate subgroup. This borrowing of information tends to move the extreme NA subgroup

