more towards the study mean [11] but by acknowledging between group variations, the uncertainty around the overall population mean result increases. Thus simply changing the statistical model to the more reasonable hierarchical (random effects model) while using the same PLATO data results in a similar combined point estimate of 0.86 but with 95% CI 0.49 to 1.60. It is worth taking a moment to fully understand what these intervals from the 2 different models are actually providing and recognizing the important differences. For the original NEJM analysis, the point estimate and confidence interval have assumed no between region variation and the result thus provides the best estimate of a common treatment effect, and the confidence interval depicts the uncertainty around this estimate. For the hierarchical model, the point estimate and confidence interval have acknowledged the between region variation and the result provides an estimate of the average treatment effect, and the confidence interval depicts the uncertainty around this estimate. Ignoring heterogeneity, such as possible regional variation, may lead to a false sense of certainty with an overly precise summary result (that is, the confidence interval is too narrow) and may incorrectly imply that a common treatment effect exists when actually there are meaningful differences in treatment effectiveness across regions. Finally, as has been cogently argued by others[16] with hierarchical models it appropriate to consider not only the average result but also the prediction interval which gives the range of possible values of the next study. The prediction interval for the next ticagrelor / clopidogrel study is very wide (0.86, 95%CI 0.24 – 3.34) providing additional justification for this proposal.

The use of Bayesian hierarchical modeling also allows the formulation of probability statements.

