All patients hospitalized for an ACS, with or without ST-segment elevation, will be eligible to participate. For STEMI and NSTEMI positive biomarkers and appropriate ECG changes will be required. NSTEMI patients with negative biomarkers are generally considered as unstable angina and will also be eligible for study inclusion if their treating physician has determined that DAPT is appropriate. It is important to note that the entrance criteria of this study are well aligned with those of PLATO allowing synthesis of the totality of the evidence (see analysis section below).

The intervention

Patients will be randomly assigned to receive standard doses of ticagrelor or clopidogrel. Ticagrelor will be given according to PLATO dose[9] of a 180 mg loading dose followed by 90 mg BID. Clopidogrel patients will receive a 300-mg loading dose followed by 75 mg daily. All patients will receive aspirin loading dose of 325 mg followed by 81 mg daily. Patients will be encouraged to take their DAPT medication for 12 months. Patient compliance will be monitored electronically via the provincial drug formulary. This will allow for the assessment for any specific DAPT interactions, particularly with anticoagulants. This is of clinical importance since bleeding is the main adverse outcome associated with DAPT.

[figure not shown]
Study outcomes

The main outcome will be a composite of total mortality, myocardial infarction (MI), or stroke at 12 months (PLATO primary outcome). Secondary outcomes will be cardiovascular mortality, stroke, major bleeding requiring hospitalization, recurrent coronary revascularizations, patient compliance and drug side effects. Clinical events will be independently assessed from hospital and provincial electronic health records which have been previously validated for these outcomes[25-27]. Data extraction will be by blinded observers so the initial unblinding of treatment assignment should not result in bias. At the time of consent, patients

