The main risk or limitation to this study is whether a single center is able to produce compelling, practice altering research. Here the trade-off is between maximizing generalizability by performing a multicenter trial and respecting economic realities and feasibility. It must also be recognized that evidence from this study will not be considered in isolation but in combination with pre-existing evidence. As previously discussed, this study will provide as much, and likely at least 50% more, evidence for NA patients than presently exists. Importantly, this single center is representative of most Quebec hospitals. Also, there is objective evidence of a single center performing a practice altering pragmatic RCT. The pragmatic HEAT trial[36], comparing antithrombotic therapy with bivalirudin or unfractionated heparin for PCI, recruited 1917 patients (97% of possible total) from a single center in 20 months and showed an increased risk (RR 1.52, 95% CI 1.09–2.13, $p=0.01$) in the primary efficacy outcome (a composite of all-cause mortality, cerebrovascular accident, reinfarction, or unplanned target lesion revascularization) with the much more expensive bivalirudin. This trial has been pivotal not only in the clarifying the role, or lack thereof, of bivalirudin but also in furthering the debate about matching ethical concerns of informed consent in pragmatic RCTs with the degree of risk involved[42]. Another risk or limitation is our dependency on administrative databases for evidence of ongoing drug exposure and outcome data. This dependency on electronic databases is an innovative use of data science to render feasible clinical experimentation. Critics may fear that these measures are not as reliable as direct measures obtained during scheduled research mandated clinical encounters. However ample research into the use of the Quebec administrative databases has repeatedly confirmed their reliability for drug exposure[43] and hard outcomes, particularly for cardiovascular outcomes[25, 27]. Typically, conventional RCTs do not measure drug exposure, other than occasional isolated pill counts, and so monthly evidence of drug purchases, while not perfect, should give an as good as, or likely better, proxy to compliance. Also RCTs often have trouble recording side effects but the systematic nature of these databases should assure that all clinically meaningful adverse accounts are captured. Of course any baseline differences between the 2 intervention arms should be balanced by the randomization process. Another limitation is our inability to simultaneously address other pertinent and related ACS questions. For example, prasugrel is another antiplatelet agent but we didn't have the power for a 3 way comparison and the additional complexity was seen as a barrier to obtaining a definitive answer. Therefore, we selected to investigate what are arguably the 2 principal competing DAPT interventions. The preferred aspirin DAPT dose also remains unknown and while a 2nd randomization to low or high dose aspirin might address that, it was felt that the additional complexity and limited power to answer this type of interaction would again distract from our principal research question.

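### The main Bayesian analysis takes PLATO's North American patients as its prior with no between-study variance, although the protocol itself argues that effects vary between populations

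*Protocol*

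**What the plan says.** - **Role of the prior.** The end of Sample size calculations makes the 1,800 PLATO NA patients the prior for the main Bayesian analysis and counts them as a safety margin of more than 50%. Statistical analysis makes PLATO prior times current likelihood the primary analysis, described as "a mathematically rigorous and exact combination of the totality of the data". Neither place mentions a discount or a between-study term.
- **Other analyses planned.** Statistical analysis adds a standalone Bayesian analysis with a non-informative prior. Anticipated results and conclusions says that both the whole-PLATO prior and the NA prior will be examined, and that the whole-PLATO prior is less definitive than the published result because regions vary.
- **Basis for combining.** Study population states that "the entrance criteria of this study are well aligned with those of PLATO allowing synthesis of the totality of the evidence". No other ground is offered.
- **The protocol's view of heterogeneity.** Knowledge to date doubts that PLATO patients respond identically "given recruitment, genetic and background treatment variations". It explains that hierarchical borrowing pulls the extreme NA result towards the overall mean, and adds: "The prediction interval for the next ticagrelor / clopidogrel study is very wide (0.86, 95%CI 0.24 – 3.34").

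**The concern.** TC4 is the next study to which that prediction interval refers. The background section argues for shrinking the NA result and for allowing a new study to differ from earlier ones. The main analysis, as described, does neither. It takes the NA estimate at its published location and precision, as if the TC4 effect and the PLATO NA effect were the same parameter. Crediting 1,800 historical patients one for one towards the sample size makes the same assumption.

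If that assumption fails, the main result is pulled towards 1.25 and its interval is too narrow. The headline probability then depends on a between-study variance that has been left implicitly at zero.

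**Working it through.** **Inputs from the protocol.** NA subgroup HR 1.25 (0.93-1.67). Hierarchical mean effect 0.86 (0.49-1.60). Prediction interval 0.86 (0.24-3.34). Event rates 12% and 10%. Planned total 4,000; illustrative total 1,500.

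**Assumptions.** Normal approximation on the log scale, equal allocation, clustering ignored, and the risk ratio 10/12 treated as a hazard ratio.

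**1. The plan's own figure.** Anticipated results and conclusions gives 99% probability that clopidogrel is superior, using the NA prior and 1,500 concordant patients.
- Prior SE = ln(1.67/0.93)/3.92 = 0.149.
- Events: 750 × 0.12 = 90 and 750 × 0.12 × 1.25 = 112.5. Likelihood SE = √(1/90 + 1/112.5) = 0.141.
- Posterior SE = (1/0.149² + 1/0.141²)^(-1/2) = 0.103. P(HR > 1) = Φ(ln 1.25/0.103) = 98.5%.
- With a between-study SD of 0.2 added to the prior the figure is 96.5%, and with 0.6 it is 94.7%.

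The stated 99% therefore fits an undiscounted NA prior. That is consistent with no discount but does not prove it.

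**2. Between-region SD implied by Knowledge to date.**
- SE of the mean effect = ln(1.60/0.49)/3.92 = 0.302.
- Predictive SD = ln(3.34/0.24)/3.92 = 0.672.
- Implied SD = √(0.672² − 0.302²) = 0.600.

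**3. Effect on the main result at 4,000 patients.**
- Events = 2,000 × 0.12 + 2,000 × 0.10 = 440. Trial SE = 2/√440 = 0.095.
- Trial estimate = ln(10/12), ratio 0.83.
- Prior variance = 0.149² + SD². Prior weight = (1/prior variance)/(1/prior variance + 1/0.095²).

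| Analysis | Prior weight | Posterior HR | P(ticagrelor better) |
|---|---|---|---|
| NA prior, SD 0 | 29% | 0.94 | 0.79 |
| NA prior, SD 0.2 | 13% | 0.88 | 0.93 |
| NA prior, SD 0.6 | 2% | 0.84 | 0.97 |
| Predictive prior centred on 0.86 | 2% | 0.83 | 0.97 |
| Standalone | 0% | 0.83 | 0.97 |

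Clustering would enlarge the trial SE and so raise the prior's share above these figures.

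**4. The safety margin.** Taken one for one, 1,800/4,000 = 45%, and 1,800/3,000 (the individually randomised total) = 60%. With a between-study SD the prior is worth 1,800 × 0.149²/(0.149² + SD²) patients: about 644 at SD 0.2 (16% of 4,000) and about 105 at SD 0.6 (3%).

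**The case against.** The strongest reply is that the protocol already guards against over-reliance on one prior. It plans two PLATO priors and a standalone analysis, and the table shows that SD 0.6 lands almost on the standalone result. Both ends of the range are thus effectively planned. That stands, and it limits the harm. But the standalone analysis is not primary. Switching between the two PLATO sources changes where the prior is centred, not whether TC4 may differ from PLATO. The intermediate case is not covered.

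A second reply is that an NA prior for a Montreal hospital answers the regional argument, since Knowledge to date is about differences between regions within PLATO. This is fair. What remains is an unaddressed exchangeability assumption between PLATO's NA patients and TC4, not a strict contradiction.

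Third, 0.6 is a between-region SD around 0.86, not a measure of variation between NA studies, and 0.2 comes from no document. Both are right. They serve as an upper bound and an assumed middle value.

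Fourth, discounting may be specified in an analysis plan not shown here, and the protocol does mention hierarchical models. But the protocol itself names the prior, counts its patients and quotes the resulting probabilities.

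A reader might also infer more than the documents support:
- **That the regimens differ from PLATO's.** Only ticagrelor is tied to PLATO ("Ticagrelor will be given according to PLATO dose[9] of a 180 mg loading dose followed by 90 mg BID"). The clopidogrel regimen and the single aspirin regimen are given without reference to it, and Possible problems says "The preferred aspirin DAPT dose also remains unknown". But PLATO's clopidogrel and aspirin doses appear nowhere in the protocol, so no mismatch can be shown.
- **That the whole-PLATO prior is also undiscounted.** The text describes it as widened for regional variation, so the point is confined to the NA prior.
- **That the word exact claims identical patients or treatments.** In context it describes Bayesian updating as opposed to p values, and it can stay.

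**Conclusion.** The point holds for the NA prior in the main analysis. That prior is used with no stated between-study variance, on a compatibility argument that rests on entrance criteria alone, although the protocol argues for heterogeneity and quotes a very wide prediction interval for the next study. On the planning figures, leaving the variance at zero moves the result from HR 0.83 with probability 0.97 to HR 0.94 with probability 0.79.

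This rests on a normal approximation, 440 events, no clustering, and trial data falling exactly at the planning ratio. The absence of a discount is inferred from the text's silence and from the match between 98.5% and the stated 99%. It should be put right before the data are analysed. It does not invalidate the trial, because the standalone result will be available. Nothing here judges any dose.

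**What to change.** - **Primary synthesis (Statistical analysis).** Specify a hierarchical model in which TC4 is a further exchangeable group alongside the PLATO regions, or equivalently a prior that carries a between-study variance term.
- **Sensitivity range.** Report the NA-prior result at between-study SD 0, 0.2 and 0.6. Label 0.2 as an assumption and 0.6 as an upper bound taken from the protocol's own prediction interval.
- **Standalone analysis.** Keep it as planned.
- **Safety margin (Sample size calculations).** State that a margin of more than 50% holds only if PLATO's NA patients and TC4 patients are fully exchangeable.

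The cost is protocol wording and a few model runs, with no extra patients. The downside is a wider combined interval and a smaller claimed margin. At an SD near 0.6 the synthesis would add little to the standalone result, and the protocol should say so.
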